## **6.7. Compliance with Study Treatment Administration**

When participants are dosed at the site, they will receive study treatment directly from the investigator or designee, under medical supervision. The date and time of each dose administered in the clinic will be recorded in the participant’s eCRF. The dose of study treatment and study participant identification will be confirmed at the time of dosing by a member of the study site staff other than the person administering the study treatment.

When participants self-administer oral study treatments at home, compliance with CAB + RPV dosing will be assessed through querying the participant during the site visits and documented in the source documents and CRF. IP accountability will be evaluated using pill counts of unused IP (CAB and RPV tablets). This assessment will be conducted each time the participant receives a new (refill) supply of oral study medication, completes the oral lead-in or any oral bridging phase. A record of the number of CAB and RPV tablets dispensed to and taken by each participant must be maintained and reconciled with study treatment and compliance records. Treatment start and stop dates will also be recorded in the eCRF.

Due to the long acting nature of the CAB LA and RPV LA it will be imperative that the participant is compliant with dosing instructions. As part of the screening and participant selection process, it is imperative that Investigators discuss with potential participants the

long-term commitments for the trial, and the importance of adhering to treatment regimens. Sites are to have plans in place for adherence counselling for both treatment arms of the study for the duration of the study including the LTFU Phase. In addition, Investigators must have plans in place to perform visit reminders, utilizing patient trackers provided by the study team as needed, and to verify the participant's contact information at each visit. Investigators should contact patients directly in the event that a participant misses any scheduled visit.

## **6.8. Protocol Permitted Substitutions**

### **6.8.1. Oral Bridging**

In exceptional circumstances, to address pre-planned missed CAB LA + RPV LA dosing visits, in consultation with the medical monitor, Investigators may provide daily oral CAB 30 mg and RPV 25 mg as a short-term “bridging” strategy for participants who have begun CAB LA + RPV LA. In certain circumstances (e.g., prior to steady state dosing and following a >4 week oral bridge) repeating the loading doses of CAB IM and RPV IM may be required. **Participants who withdraw during an oral treatment period must be initiated on HAART therapy within 24 hours after the last oral treatment with CAB + RPV.** Should a participant require “oral bridging”, sites must contact the study Medical Monitor for guidance with treatment and dosing strategies prior to a missed CAB LA + RPV LA dose.

Please refer to [Appendix 10](#) in Section [11.10](#) for study management information during the COVID-19 pandemic.

## **6.9. Interruption of Study Treatment and Visit/Dosing Windows**

IP may be interrupted at the discretion of the Investigator in the event of an AE, according to the severity of the AE.

If one or more antiretroviral medications is held due to toxicity or adverse events, all antiretroviral medications must be held to reduce the risk of development of resistance taking into account both the length of the planned interruption and the pharmacokinetic half-life of each antiretroviral of the regimen, in a way to minimize the risk of development of resistance.

**It is important to note that keeping to the participant's visit schedule is a very important component to the study.**

**Note: All decisions regarding dose interruption / resumption must be discussed with the Medical Monitor in advance.**

### **6.9.1. IM Dosing**

Participants receiving CAB LA and/or RPV LA are anticipated to be at risk for development of virologic resistance if ART is interrupted. The time period during which participants are at risk for development of virologic resistance may be determined by the period between when drug levels fall below therapeutic values and when they fall below

levels which exert selective pressure on HIV. This time period will vary by ART agent and is dependent upon effective concentration, inhibitory concentration, and half-life. Plasma concentrations of both LA drugs may be measurable for more than one year following IM injections. Any interruption in IM dosing should be discussed with the Medical Monitor. Investigators should ensure that the participant initiates alternative highly active ART to minimize the risk of developing resistance as concentrations of CAB and RPV decline over time.

IM dosing is expected to occur during the week in which the participant's projected visit falls (as according to the date of the first injection). The first injections for participants from ATLAS on CAB LA + RPV LA Q4W will occur at Day 1. The first injections for participants transitioning from oral SOC are administered at Week 4b (can be performed as soon as lab results from Week 4a become available and should be performed where possible within 2 weeks of visit 4a), and the second injections are given at Week 8. Between the Week 4a and 4b visits, participants must continue daily treatment with oral CAB and RPV tablets.

Since the first injection visit (Day 1 or 4b) will determine the future injection visit schedule for participants, planning for the first injection visit date (within allowed visit windows) should take into consideration the availability of the participants to adhere to future visit windows (planned vacations, business trips, *etc.*).

**CAB LA + RPV LA dosing for participants transitioning from SOC treatment is as follows:**

All injections should be planned as single injections per drug.

**6.9.1.1. IM injections every 4 weeks (Q4W):**

Week 4b only - CAB LA 600 mg + RPV LA 900 mg, each given as 1 X 3 mL IM injection

Week 8 and Q4W thereafter - CAB LA 400 mg IM + RPV LA 600 mg IM every 4 weeks for 100 weeks, each given as 1 X 2 mL IM injection

At Week 4b, participants transitioning from SOC will return to the clinic, take the last dose of oral CAB 30 mg + RPV 25 mg, and receive the first CAB LA 600 mg + RPV LA 900 mg injections (within 2 hours of the final oral dose of CAB + RPV). The first injection visit with IM CAB LA + RPV LA at Week 4b can be performed once central lab results are available and safety parameters are reviewed from the Week 4a visit.

The second and third IM injections with CAB LA 400 mg and RPV LA 600 mg will be performed at Week 8 and Week 12. There will be a -7 day dosing window for the second and third IM injections such that the second injection occurs within the window of Week 7 and Week 8 but no later than Week 8 and the third injection occurs within the window of Week 11 and Week 12 but no later than Week 12. Subsequent injections with CAB LA 400 mg and RPV LA 600 mg will occur every 4 weeks ( $\pm 7$  days) thereafter. In addition, starting after the Week 16 injection, efforts should be made to limit time between injection visits to a maximum of 5 weeks. The Medical Monitor must be

contacted if the length of time between injections exceeds or is projected to exceed 5 weeks.

#### **6.9.1.2. IM injections every 8 weeks (Q8W):**

Week 4b – CAB LA 600 mg + RPV LA 900 mg IM, each given as 1 X 3 mL IM injection

Week 8 - CAB LA 600 mg + RPV LA 900 mg IM, each given as 1 X 3 mL IM injection

Week 16 and Q8W thereafter - CAB LA 600 mg + RPV LA 900 mg IM, every 8 weeks for 100 weeks, each given as 1 X 3 mL IM injection

At Week 4b, subjects will return to the clinic, take the last dose of their oral (CAB 30 mg + RPV 25 mg), and receive the first CAB LA (600 mg) + RPV LA (900 mg) injections (within 2 hours of the final oral dose of CAB + RPV). The first injection visit with IM CAB LA + RPV LA at Week 4b can be performed once central lab results are available and safety parameters are reviewed from the Week 4a visit.

The second loading injection will be administered at Week 8 (CAB LA 600 mg + RPV LA 900 mg, with subsequent injections (CAB LA 600 mg + RPV LA 900 mg) occurring every 8 weeks thereafter. The dosing window for the second injection allows administration between Week 7 and Week 8, but preferably not later than Week 8. After Week 16, a dosing window ( $\pm 7$  days) for injections is allowed, but not preferred. Starting at the Week 16 injection, the interval between injection visits should be limited to a maximum of 9 weeks. If the length of time between injections exceeds, or is projected to exceed 9 weeks, the Medical Monitor must be contacted to discuss individual subject case management

#### **Participants transitioning from ATLAS and currently receiving CAB LA + RPV LA Q4W**

Patient transitioning from the ATLAS study and on CAB LA + RPV LA Q4W treatment will be randomized at Day 1 to either continue Q4W administration or transition to Q8W administration of CAB LA + RPV LA. The first injection visit for the ATLAS-2M study can be performed once the final central lab results from the ATLAS study are available and safety parameters have been reviewed. For participants who received three or more Q4W CAB LA + RPV LA injections within ATLAS, the transition from ATLAS to ATLAS-2M Day 1 dosing must occur 4 weeks ( $\pm 7$  days) from the final injections received in ATLAS. For those who received less than three Q4W injections within ATLAS, this transition to ATLAS-2M Day 1 injections must occur within 4 weeks (-7 days) from the final ATLAS injections

Dosing for participants transitioning from CAB LA + RPV LA Q4W in ATLAS is as follows:

**6.9.1.3. IM injections every 4 weeks (Q4W) (Q4W from ATLAS Q4W):**

Starting at Day 1, all injections will continue with the maintenance dose of CAB LA 400 mg and RPV LA 600 mg administered every 4 weeks ( $\pm 7$  days). In addition, efforts should be made to limit time between injection visits to a maximum of 5 weeks. The Medical Monitor must be contacted if the length of time between injections exceeds or is projected to exceed 5 weeks.

**6.9.1.4. IM injections every 8 weeks (Q8W) (Q8W from ATLAS Q4W):**

Participants transitioning from ATLAS and receiving CAB LA + RPV LA Q8W will initiate dosing at the Day 1 visit:

Day 1- CAB LA 600 mg + RPV LA 900 mg IM, each given as 1 X 3 mL IM injection

Week 8 and Q8W thereafter- CAB LA 600 mg + RPV LA 900 mg IM, each given as 1 X 3 mL IM injection

The second injection will be administered at Week 8 (CAB LA 600 mg + RPV LA 900 mg, with subsequent injections (CAB LA 600 mg + RPV LA 900 mg) every 8 weeks thereafter. The dosing window for the second injection allows administration between Week 7 and Week 8, but preferably not later than Week 8. After Week 16, a dosing window ( $\pm 7$  days) for injections is allowed, but not preferred. Starting at the Week 16 injection, the interval between injection visits should be limited to a maximum of 9 weeks. If the length of time between injections exceeds, or is projected to exceed 9 weeks, the Medical Monitor must be contacted to discuss individual subject case management.

Any request for the visit/dosing to occur outside of the allowed window must be discussed and agreed with the Medical Monitor prior to dosing. In the event of a late dose, a revised dosing schedule for subsequent dosing may be required and will be communicated to the site staff at the time of approval for continued dosing. Temporary switch to oral dosing of CAB and/or RPV may be an option based on individual participant circumstance as described in Section 6.8.

See the SPM for scheduling guidance and further information and examples.

**Note: All decisions regarding dose interruption/ resumption must be discussed with the Medical Monitor in advance.**

**6.9.2. Oral Dosing**

The Week 4a Visit during the Oral Lead-in Phase for participants transitioning from SOC is expected to occur 4 weeks ( $\pm 3$  days) after to the Day 1 Baseline visit. However, the number of tablets dispensed should be considered when scheduling the next visit.

Any interruption in therapy (scheduling conflicts, life circumstances, *etc.*) during any oral dosing period that is greater than 7 consecutive days must be discussed with the Medical Monitor prior to resumption of therapy. The Medical Monitor must be contacted upon

site staff becoming aware of resumption in therapy, if therapy was resumed without prior approval.

Visits for participants in LTFU are expected to occur as projected according to the last injection.

### **6.10. Discontinuation of Study Treatment**

Participants unable to manage drug toxicity or tolerate investigational product (IP, either formulations of CAB or RPV) must have IP discontinued. Any participant receiving at least one dose of CAB LA and /or RPV LA who discontinues IP / Withdraw will initiate treatment with HAART enter the LTFU Phase for 52 weeks of follow-up (see Section 4.2.4).

When the CAB+RPV LA marketed product is locally available participants must enter the LTFU Phase if withdrawing for safety related reasons only. see Section 5.5.

### **6.11. Treatment of Study Treatment Overdose**

For participants receiving Oral CAB, any tablet intake exceeding a total daily dose of 30 mg will be considered an overdose. For participants receiving oral RPV, any dose exceeding a total daily dose of 25 mg will be considered an overdose.

For CAB LA and RPV LA, any single dose in excess of the studied doses will be considered an overdose.

Should IM maladministration, specifically overdose or inadvertent IV dosing, be suspected at any time, the participant will stay onsite for approximately 2-3 hours post dose for safety monitoring and an ECG will be performed at 2 hours post dose. The Medical Monitor will be notified in the event of a suspected maladministration.

In the event of suspected maladministration, additional PK samples will be drawn at 2 hours post dosing for evaluation of CAB and RPV concentrations.

For the purposes of this study, an overdose is not an AE (refer to Section 11.6.1 ) unless it is accompanied by a clinical manifestation associated with the overdose. If the clinical manifestation presents with serious criteria, the event is a SAE (see Section 11.6.2).

If an overdose occurs and is associated with an adverse event requiring action, all study medications must be temporarily discontinued until the adverse event resolves.

The Investigator should use clinical judgement in treating overdose, as ViiV Healthcare is unable to recommend specific treatment.

In the event of an overdose the investigator or treating physician should:

1. Contact the Medical Monitor immediately

2. Closely monitor the participant for adverse events (AEs)/serious adverse events (SAEs) and laboratory abnormalities until the IP can no longer be detected systemically (at least 5 days for oral CAB and oral RPV, and 52 weeks for CAB LA and RPV LA)
3. Obtain a plasma sample for pharmacokinetic (PK) analysis if possible within 2 days from the date of the last dose of study treatment if requested by the Medical Monitor (determined on a case-by-case basis).
4. Document the quantity of the excess dose as well as the duration of the overdosing in the CRF.

Decisions regarding dose interruptions or modifications will be made by the investigator in consultation with the Medical Monitor based on the clinical evaluation of the participant.

### **6.12. Treatment after the End of the Study**

The investigator is responsible for ensuring that consideration has been given to the post-study care of the participant's medical condition, whether or not GSK is providing specific post-study treatment. Participants who have successfully completed 100 weeks of treatment will continue to have access to both CAB LA and RPV LA in the Extension Phase through Week 152 and until study treatment is either locally approved and commercially available, the participant no longer derives clinical benefit, the participant meets a protocol-defined reason for discontinuation or until development of either CAB LA or RPV LA is terminated.

### **6.13. Concomitant Medications and Non-Drug Therapies**

Participants must be advised to notify their Investigator of any current or proposed concomitant medication, whether prescribed or over-the-counter, because of the potential for interactions between such treatments and the study medications. Concomitant medications (prescription and non-prescription) will be permitted during the course of the study at the investigator's discretion (except for prohibited medications described in Section 6.13.2) and should be administered only as medically necessary during the study. All concomitant medication, blood products, and vaccines taken during the study will be recorded in the eCRF. The minimum requirement is that the drug name, route, and the dates of administration are to be recorded.

Any medication or vaccine (including over-the-counter or prescription medicines, vitamins, and/or herbal supplements) that the participant is receiving at the time of enrollment or receives during the study must be recorded along with:

- reason for use
- dates of administration including start and end dates
- dosage information including dose and frequency

The Medical Monitor should be contacted if there are any questions regarding concomitant or prior therapy.

### 6.13.1. Permitted Medications and Non-Drug Therapies

Chemoprophylaxis for HIV-associated conditions is encouraged, if appropriate, at the discretion of the participant and their physician. All concomitant medications, blood products, and vaccines taken during the study will be recorded in the eCRF with dates of administration.

Because non-HIV vaccines may cause a temporary increase in the level of plasma HIV-1 RNA, it is recommended that a vaccine, if necessary, be given during or immediately after a scheduled visit after all laboratory tests have been drawn. This approach will minimize the risk of non-specific increases in the level of plasma HIV-1 RNA at the next scheduled assessment.

Other IM injectables (with exceptions below) are permitted but must be administered away from the site of IP administration (should be spaced 2 cm or more away from site of IP injection).

#### **Antacid and H2 Antagonist Use:**

Since co-administration of oral CAB and RPV is required in this study, the most restrictive dosing requirements must be taken into consideration.

**CAB oral administration only:** Antacid products containing divalent cations (e.g., aluminium, calcium and magnesium) must be taken at least 2 hours before or at least 4 hours after CAB.

Concurrent administration of multivitamins is acceptable.

**RPV oral administration only:** Antacid products must be taken at least 2 hours before or at least 4 hours after RPV. H2-Receptor antagonists (e.g. cimetidine, famotidine, nizatidine, ranitidine) may cause significant decreases in RPV plasma concentrations. H2-receptor antagonists should only be administered at least 12 hours before or at least 4 hours after RPV. RPV should not be co-administered with proton pump inhibitors, such as esomeprazole, lansoprazole, omeprazole, pantoprazole, rabeprazole.

**RPV:** Administration of clarithromycin, erythromycin and telithromycin is not recommended with RPV due to possible increase in plasma concentration of RPV due to CYP3A enzyme inhibition. Where possible, alternatives such as azithromycin should be considered. Please refer to the local rilpivirine prescribing information for guidance regarding other drugs that are prohibited, should be used with caution, require dose adjustment, or increased clinical monitoring if taken with rilpivirine.

Drugs with a known risk of Torsade des Pointes (TdP) should be used with caution when on rilpivirine (see SPM for list of drugs associated with TdP).

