31. Any acute laboratory abnormality at Screening, which, in the opinion of the investigator, would preclude the participant's participation in the study of an investigational compound
32. Participant has estimated creatine clearance  $< 50$  mL/min per  $1.73\text{m}^2$  via Chronic Kidney Disease-Epidemiology Collaboration (CKD-EPI) Method
33. Alanine aminotransferase (ALT)  $\geq 3 \times$  ULN

Concomitant Medications

34. Exposure to an experimental drug (with the exception of those in the ATLAS study including CAB, CAB LA, and RPV LA) or experimental vaccine within either 30 days, 5 half-lives of the test agent, or twice the duration of the biological effect of the test agent, whichever is longer, prior to Day 1 of this study;
 
35. Treatment with any of the following agents within 28 days of Screening:
 
 
• radiation therapy;
 
• cytotoxic chemotherapeutic agents;
 
• tuberculosis therapy with the exception of isoniazid (isonicotinylhydrazid, INH);
 
• anti-coagulation agents;
 
• Immunomodulators that alter immune responses such as chronic systemic corticosteroids, interleukins, or interferons. Note: Participants using short-term (e.g. <math>\leq 21</math> days) systemic corticosteroid treatment; topical, inhaled and intranasal corticosteroids are eligible for enrolment.
 
 
36. Treatment with an HIV-1 immunotherapeutic vaccine within 90 days of Screening
 
37. Treatment with any agent, except recognized ART as allowed above, with documented activity against HIV-1 within 28 days of study Day 1. Treatment with acyclovir/valacyclovir is permitted.
 
38. Use of medications which are associated with Torsade de Pointes. (See SPM for a list of relevant medications)
 
39. Current or prior history of etravirine (ETR) use
 
40. Current use of tipranavir/ritonavir or fosamprenavir/ritonavir
 
41. Participants receiving any prohibited medication and who are unwilling or unable to switch to an alternate medication. Note: Any prohibited medications that decrease CAB or RPV concentrations should be discontinued for a minimum of four weeks or a minimum of three half-lives (whichever is longer) prior to the first dose and any other prohibited medications should be discontinued for a minimum of two weeks or a minimum of three half-lives (whichever is longer) prior to the first dose

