**Participants must be discontinued from study treatment for any of the following reasons:**

- Participants who are not eligible to continue into the Maintenance Phase.
- Participants who are not eligible, or do not wish to continue on to the Extension Phase.
- Virologic withdrawal criteria as specified in Section 5.5.4 are met;
- Participant requires substitution of ART;
- Participant requires substitution or dose reduction of CAB LA or RPV LA (oral bridging supply and potential for a second loading dose may be permissible following discussion with the Medical Monitor).
- Liver toxicity where stopping criteria are met and no compelling alternate cause is identified (see Section 5.5.1);
- Renal toxicity are met and no compelling alternate cause is identified;
- QT interval (QTc) interval >550 msec from three or more tracings separated by at least 5 minutes and considered causally related to IP.
- Grade 4 clinical AE considered causally related to study drug;
- Participant has a Grade 3 or higher rash or Grade 2 rash with evidence of systemic involvement and no compelling alternative cause is identified
- Participant withdrew consent

Efficacy data for participants withdrawing from the study will be considered evaluable up to the point at which they are withdrawn using the same criteria for evaluability as for participants who complete the study.

Safety data for all participants who receive any amount of study drug, including participants who withdraw from the study, will be included in evaluations of safety.

All data from the Withdrawal visit will be recorded, as they comprise an essential evaluation that should be done prior to discharging any participant from the study.

The following actions must be taken in relation to a participant who fails to attend the clinic for a required study visit:

- a. The site must attempt to contact the participant and re-schedule the missed visit as soon as possible.
- b. The site must counsel the participant on the importance of maintaining the assigned visit schedule and ascertain whether or not the participant wishes to and/or should continue in the study.

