### 5.5.2. QTc Stopping Criteria

A participant who has a QTc interval >550 msec considered causally related to IP will be withdrawn from the study. The QTc should be based on averaged QTc values of triplicate electrocardiograms obtained over a brief (e.g., 5 to 10 minute) recording period.

If an alternative cause of the QT prolongation is determined (e.g., participant receiving drug known to cause prolonged QT or TdP), the IP may be restarted (or continued) after consultation and agreement with the Medical Monitor. RPV and RPV LA should not be administered to patients who are receiving a drug known to be associated with TdP.

When performing ECGs, the *same* QT correction formula *must* be used for *each individual participant* to determine eligibility for, and discontinuation from, the study. This formula may not be changed or substituted once the participant has been enrolled.

For example, if a participant is eligible for the protocol based on QTcB, then QTcB must be used for discontinuation of this individual participant as well.

Once the QT correction formula has been chosen for a participant's eligibility, the *same formula* must continue to be used for that participant *for all QTc data being collected for data analysis*. Safety ECGs and other non-protocol specified ECGs are an exception.

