Should IM maladministration be suspected at any time (e.g., suspected under or overdose or inadvertent IV dosing), the investigator may consider requesting the participant stay onsite for approximately 2-3 hours post dose for safety monitoring and notifying the Medical Monitor. An ECG or any other supportive testing may be obtained at the discretion of the investigator. Additionally, a PK sample may be drawn approximately 2 hours post dosing for future evaluation of CAB and RPV plasma concentrations.

Additional dosing instructions and considerations can be found in the SPM.

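### The protocol contradicts itself on giving rilpivirine with Torsade-associated drugs and on what must be done after a suspected overdose or inadvertent intravenous injection

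*Protocol*

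**What the plan says.** **Torsade-associated co-medication.** Section 5.5.2 (QTc Stopping Criteria) states that "RPV and RPV LA should not be administered to patients who are receiving a drug known to be associated with TdP". The sentence just before it deals with QT prolongation that has another cause. It gives a QT-prolonging or Torsade-associated drug as the example, and says that "the IP may be restarted (or continued) after consultation and agreement with the Medical Monitor". Section 6.13.1, under permitted medications, says that drugs with a known Torsade risk "should be used with caution when on rilpivirine" and points to a list in the Study Procedures Manual. Section 6.13 leaves concomitant medication to the investigator except for what Section 6.13.2 prohibits, and Section 6.13.2 does not name these drugs. At entry, exclusion criterion 38 in Section 5.2 is "Use of medications which are associated with Torsade de Pointes".

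**Suspected maladministration.** Section 6.11 covers suspected overdose and inadvertent intravenous dosing and says that "the participant will stay onsite for approximately 2-3 hours post dose for safety monitoring and an ECG will be performed at 2 hours post dose". It adds that pharmacokinetic samples will be drawn at 2 hours and that the Medical Monitor will be notified. Section 6.6.1 covers underdose, overdose and inadvertent intravenous dosing. It says that the investigator may consider keeping the participant onsite and notifying the Medical Monitor, that "An ECG or any other supportive testing may be obtained at the discretion of the investigator", and that a pharmacokinetic sample may be drawn.

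**QTc above 550 msec.** Among the reasons for mandatory discontinuation, Section 5.5 lists a QTc above 550 "msec from three or more tracings separated by at least 5 minutes and considered causally related to IP". Section 5.5.2 says "The QTc should be based on averaged QTc values of triplicate electrocardiograms obtained over a brief" period, with 5 to 10 minutes as the example.

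**The concern.** Both topics are safety instructions that a site has to apply at once, and the answer depends on which section is opened. A site working from Section 6.13 would allow a Torsade-associated drug with caution and go on injecting. A site working from Section 5.5.2 would not give rilpivirine. After a suspected intravenous injection, one site would regard the ECG and blood sample as required and another as optional.

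The product makes the first conflict harder to put right afterwards. Section 2.3.1 says that rilpivirine can remain in the circulation for months, and in some participants for more than a year, so an injection given under the wrong rule cannot be taken back. For the second conflict, Section 2.3.1 itself raises accidental partial intravenous injection as a possible explanation for systemic reactions with high rilpivirine concentrations. The protocol therefore treats the event as a real risk, yet does not say consistently what must follow it.

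**Working it through.** The protocol gives no figure to reproduce here. The check is a comparison of current text; none of it comes from the amendment log.

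**1. Torsade-associated drugs**

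- Section 5.5.2: rilpivirine, oral or long-acting, not to be given to someone receiving such a drug. The wording carries no restriction to a phase or to a prior QT event.
- Section 6.13.1: such drugs may be used with caution while on rilpivirine.
- Section 6.13.2 and its subsections: not named as prohibited.

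For a participant on study who needs such a drug, the first rule withholds rilpivirine and the second does not. Section 6.13.1 refers to a list of Torsade-associated drugs, so nothing suggests that the two sections mean different classes of drug.

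Section 5.5.2 is also unclear within itself. A Torsade-associated drug is its example of an alternative cause after which investigational product may be restarted or continued, and Section 6.1 includes both rilpivirine formulations in that term. The next sentence bars rilpivirine for a patient on such a drug. The two fit together if the drug has first been stopped, but the text does not state that condition, and the option to continue sits badly with it.

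**2. Suspected overdose or inadvertent intravenous dose**

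| Step | Section 6.11 | Section 6.6.1 | Section 2.3.1 risk tables |
|---|---|---|---|
| Onsite stay, 2-3 hours | required | optional | not mentioned |
| ECG | required at 2 hours | optional | optional |
| Pharmacokinetic sample, about 2 hours | required | optional | optional |
| Medical Monitor notified | required | optional | required |

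All three places cover overdose and intravenous dosing; underdose appears only in Sections 6.6.1 and 2.3.1. Section 6.11 also differs within itself. Its running text requires 2-hour samples after suspected maladministration, while its numbered overdose steps ask for a sample within 2 days, if possible and if the Medical Monitor requests it.

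**3. QTc above 550 msec (minor)**

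- Reading. Section 5.5: three or more tracings at least 5 minutes apart, averaging not mentioned. Section 5.5.2: the average of a triplicate over a brief period. Three tracings at least 5 minutes apart span at least 2 × 5 = 10 minutes, which is the upper end of the 5 to 10 minute example.
- Action. Section 5.5: discontinuation of study treatment. Section 5.5.2: withdrawal from the study. Section 5.5 itself separates the two, because participants who stop treatment in the Extension Phase before local marketing are not counted as withdrawn from the study; they enter long-term follow-up.

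**The case against.** **The Torsade conflict is narrower than it looks.** Exclusion 38 is an entry criterion, and an entry bar stricter than on-study handling is common. That stands, so exclusion 38 is context and not a third conflicting rule. The ban in Section 5.5.2 can also be read as limited to participants who have already had QT prolongation. Its position supports that reading, but its wording is general and the limit is not written, so the conflict with Section 6.13.1 remains.

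**Section 6.11 is the specific overdose section and might be taken to govern.** Nothing says so. Section 6.6.1 names the same events, and a site giving an injection is likely to consult the dosing section.

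**A reader might infer that the two QTc descriptions classify the same participant differently.** Take an invented triplicate of 540, 550 and 580 msec. The mean is 1670 / 3 = 556.7, above 550, while only one tracing exceeds 550. The decisions diverge only if Section 5.5 requires every tracing to exceed 550, and it does not say that. Three tracings 5 minutes apart, averaged over 10 minutes, satisfy both sections. On the reading this is ambiguity, not contradiction; the difference in the stated action remains.

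**A reader might infer that the PK-ECG safety evaluation is left with selectively missing data.** The documents do not support this. Section 2.3.1 ties the correlation with ECG changes to scheduled 2-hour samples at early timepoints and treats the unscheduled sample separately, as one for future evaluation. Section 3 lists no PK-ECG endpoint.

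**A reader might size the problem from the rate of under 0.5% in Section 2.3.1**, as 0.005 × 1020 = 5.1 participants. That rate counts systemic reactions after long-acting rilpivirine in clinical trials. Suspected maladministration is a different event and also includes errors with cabotegravir and overdoses, so the figure does not apply.

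**Conclusion.** The concern holds in two places. Section 5.5.2 bars rilpivirine in a patient on a Torsade-associated drug while Section 6.13.1 allows the combination with caution. For suspected overdose or intravenous dosing, Section 6.11 requires steps that Section 6.6.1, and in part Section 2.3.1, leave optional. The differing descriptions and actions for a QTc above 550 msec are a minor matter of alignment.

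The documents give no basis for a number of participants affected. The consequence is inconsistent safety handling between sites; the primary endpoint analysis is not affected.

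Two limits apply. Section 7.4.5.9 (QTc Prolongation) is in the contents list but lies in the part of the protocol not available, and the Study Procedures Manual with its drug list was not available either. Both could add detail, but neither would make the sections compared here agree as written.

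**What to change.** State each rule once and have the other sections refer to it:

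- reconcile Section 5.5.2 with Section 6.13.1, carry the outcome into Section 6.13.2 if needed, and make clear within Section 5.5.2 how its restart sentence relates to the sentence that follows;
- reconcile Sections 2.3.1 and 6.6.1 with Section 6.11 on the onsite stay, ECG, pharmacokinetic sample and Medical Monitor notification, say whether underdose falls under the same rule, and align the two sampling statements within Section 6.11;
- align Sections 5.5 and 5.5.2 on how the QTc value is obtained and on whether the action is to stop treatment or to withdraw from the study.

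Check the result against Section 7.4.5.9. The choice of clinical rule in each case belongs to the sponsor and is not proposed here. The cost is wording in the next amendment and a memo to sites; no analysis or sample size changes.
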